IRO REC'D AUG 23 2018

**UNIVERSITY OF WASHINGTON SCHOOL OF MEDICINE
FRED HUTCHINSON CANCER RESEARCH CENTER
SEATTLE CANCER CARE ALLIANCE**

**A Response-Adapted Clinical Trial of Weekly Carfilzomib with or without Rituximab for
Waldenström's Macroglobulinemia and Marginal Zone Lymphoma**

Principal Investigator: [name]
Associate Professor, University of Washington
Associate Member, Fred Hutchinson Cancer Research Center
Seattle Cancer Care Alliance

Statistical Consultant
[name]

Version: 4.0, Date 08/01/2018

This trial is supported by a grant from the NCCN.

FHCRC IRB Approval

OCT 02 2018

Document Released Date

SCHEMA

Registration: WM and MZL, N=24. (At least 5 Rituximab-refractory)

Carfilzomib (CFZ) for two, 28 day-cycles as follows:

CFZ 20 mg/m² as a 30-min IV infusion on Day 1 of cycle 1

If tolerated, CFZ 56 mg/m² as a 30-min IV infusion on Days 8 and 15 of cycle 1

If tolerated, CFZ 70 mg/m² as a 30-min IV infusion on Days 1, 8, and 15 of cycle 2

Assess paraprotein and/or nodal response; BM Bx (research)

If minimal response (MR: 25% or greater m-protein reduction) for WM, or PR for MZL: continue CFZ x 4 more cycles at 70 mg/m² dose level (days 1, 8, and 15) as tolerated.

If not: Continue CFZ x 4 more cycles at 70 mg/m² dose level if tolerated, and add rituximab 375 mg/m² weekly x 4 doses (cycle 3) then monthly (cycles 4-6)

Note: Study to be stopped for futility if < 3 of the first 9 subjects achieve initial response with CFZ alone

Note: Study accrual to be suspended if cardiotoxicity limits are exceeded, or rituximab cannot be delivered per protocol (see section 12)

Stop therapy after 6 total CFZ cycles: Surveillance for up to 1 year (measured from time of study drug start)

TABLE OF CONTENTS

1.0 OBJECTIVES..... 4

2.0 BACKGROUND..... 4

3.0 DRUG INFORMATION..... 5

4.0 STAGING CRITERIA..... 6

5.0 ELIGIBILITY CRITERIA..... 6

6.0 REGISTRATION..... 7

7.0 TREATMENT PLAN..... 7

8.0 REQUIREMENTS TO BEGIN A NEW CYCLE AND DOSAGE MODIFICATIONS..... 9

9.0 CONCOMITANT THERAPY..... 12

10.0 STUDY PROCEDURES..... 13

11.0 CRITERIA FOR EVALUATION AND ENDPOINT DEFINITIONS..... 14

12.0 STATISTICAL CONSIDERATIONS..... 14

13.0 CORRELATIVE STUDIES..... 15

14.0 REPORTING REQUIREMENTS FOR ADVERSE EVENTS/ADVERSE REACTIONS..... 16

15.0 DATA AND SAFETY MONITORING PLAN.....20

16.0 RECORDS.....20

17.0 REGULATORY RESPONSIBILITIES OF SPONSOR-INVESTIGATOR..... 20

18.0 TERMINATION OF THE STUDY..... 21

19.0 REFERENCES 22

20.0 APPENDIX..... 24

1.0 OBJECTIVE

- 1.1 Primary Objective: Determine the overall response rate of single-agent weekly CFZ, measured after 2 cycles of therapy, in WM and MZL.
- 1.2 Secondary Objectives:
 - 1.2.1 Assess safety and tolerability of single agent, weekly CFZ in patients with WM and MZL, and determine the tolerability of weekly CFZ+rituximab for applicable patients.
 - 1.2.2 Estimate the time to best response, response duration, and survival with weekly CFZ for WM and MZL
 - 1.2.3 Evaluate the overall response rate associated with weekly CFZ in a subset of patients with rituximabrefractory WM or MZL

2.0 BACKGROUND

- 2.1 Waldenström's macroglobulinemia (WM) and marginal zone lymphoma (MZL) are incurable subtypes of non-Hodgkin lymphoma (NHL) with a protracted natural history.^{1,2} Therapy for WM and MZL, extrapolated from more common NHL subtypes, has been historically characterized by increasing toxicity of alkylating agents alone or in combination, and successively shortening remissions. WM and MZL patients present with unique features including high rates of marrow compromise in WM, paraprotein-related complications in WM, and autoimmune phenomena or infections in MZL. This context points to a significant unmet need for specific therapies for patients with WM and MZL.

Recent therapeutic advances including the successful application of rituximab, proteasome inhibitors (PI), and more recently cell signaling/kinase inhibitors.^{3,4} While these agents have improved the outlook for patients, the optimal combination, sequence, and dosing strategy of novel therapies remains undefined. Following demonstration of its activity in relapsed and refractory non-Hodgkin lymphoma in 2005, bortezomib was found efficacious in Waldenström's and carries a consensus recommendation for use in relapsed or refractory disease.⁵⁻⁷ Bortezomib produces response rates of 80% or higher, when co-administered with rituximab, in WM in relapsed/refractory and newly diagnosed patients.^{8,9} In extranodal marginal zone lymphoma (MALT lymphoma), single-agent bortezomib showed a response rate of 48%, and 6/11 patients when combined with rituximab in a smaller study, supporting further trials of proteasome inhibition in this histology.^{10,11} Thus, proteasome inhibition is a potentially effective strategy in both WM and MZL, justifying the study of this therapeutic class in both diseases.

Nonetheless, the prototype proteasome inhibitor bortezomib is associated with well-known neurotoxicity. The novel epoxyketone proteasome inhibitor carfilzomib (CFZ), with increased potency and selectivity compared to bortezomib, has shown favorable results with an attenuated risk of neuropathy in patients with WM and multiple myeloma.¹²⁻¹⁴ CFZ is currently approved for treatment of relapsed/refractory multiple myeloma in patients who have received 1 or more lines of therapy as a single agent, and in combination with dexamethasone or lenalidomide plus dexamethasone, in patients who have received 1 to 3 prior lines of therapy.

The approved dose of CFZ for relapsed/refractory multiple myeloma is as follows, and employs a priming dose and if tolerated, then escalating to 27 mg/m² (over 10 minutes) when given in combination with lenalidomide and dexamethasone, or escalating CFZ to 56 mg/m² (given over 30 minutes) when given in combination with dexamethasone:

- o CFZ in combination with lenalidomide and dexamethasone
 - o cycle 1: 20 mg/m² over 10 minutes on days 1 and 2; if tolerated, increase dose to 27 mg/m² over 10 minutes on days 8, 9, 15, and 16 of a 28-day treatment cycle
 - o cycles 2-12: 27 mg/m² over 10 minutes on days 1, 2, 8, 9, 15, and 16 of a 28-day treatment cycle

- o cycles 13-18: 27 mg/m² over 10 minutes on days 1, 2, 15, and 16 of a 28-day treatment cycle
 - CFZ in combination with dexamethasone
- o cycle 1: 20 mg/m² over 30 minutes on days 1 and 2; if tolerated, increase dose to 56 mg/m² over 30 minutes on days 8, 9, 15, and 16 of a 28-day treatment cycle
- o cycle 2 and onwards: 56 mg/m² over 30 minutes on days 1, 2, 8, 9, 15, and 16 of a 28-day treatment cycle

Results of CFZ for first-line treatment of WM in combination with rituximab and dexamethasone have recently been published in abstract form. The combination produced a response in 81% of patients, and 22/31 remain on study at 8 cycles of therapy; no neuropathy of grade 2 or higher was seen.¹² However, the single-agent efficacy of CFZ in WM or other NHL is undefined, nor have response-adapted studies--reserving combination therapy with rituximab for non-responders-- been reported.

The dosing of carfilzomib has recently undergone evolution, with implications for patient convenience and the practical administration of therapy. CFZ was historically administered twice weekly, but recent data from multiple myeloma (MM) identified acceptable safety and promising efficacy once weekly administration at the so-called 20/70 dose (CFZ 20 mg/m² over 30 minutes on Cycle 1 Day 1, then 70 mg/m² on D8 and D15 of cycle 1 and all days of future cycles; cycles are repeated every 28 days).¹⁵ In that study, only 12% of patient discontinued therapy due to adverse events. Despite limitations of cross-trial comparisons, adverse event rates were similar or lower than prior twice-weekly studies. This data, in addition to providing the basis for a large upcoming study using weekly carfilzomib in myeloma (NCT#02412878), support the proposed weekly dosing in this trial.

CFZ has been associated with cardiac toxicity in clinical trials, possibly related to co-administration of routine IV fluids, cardiac myocyte protein accumulation and oxidative damage, or combined reasons¹⁶. The rate of any-grade cardiac failure approaches 6-8% with CFZ, higher than after bortezomib although one study found no change in prospectively monitored ventricular function between these agents.^{14, 17, 18} Serial monitoring of the cardiac marker brain natriuretic peptide (BNP) has been evaluated as an early biomarker of cardiac risk, particularly in MM patients. Available data show variable sensitivity of BNP in predicting cardiac failure, and suggest further prospective study of this marker is warranted.^{16, 19} This trial requires baseline evaluation of ejection fraction and will exclude patients with inadequate cardiac function, will suspend accrual for excess cardiotoxicity as in section 12, and will hold therapy for uncontrolled systolic hypertension and include blood pressure monitoring at home for selected patients.

Overall, this will address the substantial unmet need of defining a disease-specific therapy for WM and MZL patients, clarify the efficacy and safety of single-agent carfilzomib, and employ a response-adapted strategy adding rituximab added for initial non-responders as described in section 2.2.

2.2 Response adapted therapy for WM and MZL: Rationale for the Addition of Rituximab for Initial Carfilzomib Non-responders

This approach offers promise to define the single-agent activity of CFZ, and reduce unneeded exposure to combination CFZ+ R therapy in a proportion of WM and MZL patients. In addition, this provides an opportunity to perform correlative studies which may help optimize sequencing of therapy in future studies. The addition of rituximab is supported by its known significant single agent activity in WM and MZL, with over 50% of patients responding; it is also well tolerated, and does not appear to cause additive toxicity in combination with bortezomib.²⁰⁻²²

In this trial, rituximab will be administered for subjects who fail to achieve a minimal response in WM or at least a PR in MZL, after 2 cycles of CFZ single-agent therapy. A stopping rule is included to minimize unnecessary exposure to single-agent CFZ (see section 12.0, Statistical Methods). We will assess the efficacy and safety of this approach, while simultaneously evaluating secondary endpoints (such as modulation of the risk of tumor flare in WM) and correlative hypotheses (carfilzomib may upregulate CD20 expression to prime for rituximab response). Thus study is best regarded as a phase II study, with stopping for futility, powered to evaluate the response rate of single-agent weekly CFZ in WM and MZL.

3.0 DRUG INFORMATION: Carfilzomib (CFZ) and Rituximab

3.1 CFZ is a synthetic small molecule peptide bearing the chemical name (2S)-N-((S)-1-((S)-4-methyl-1-((R)-2-methyloxiran-2-yl)-1-oxopentan-2-ylcarbonyl)-2-phenylethyl)-2-((S)-2-(2-morpholinoacetamido)-4-phenylbutanamido)-4-methylpentanamide. The molecular formula is C₄₀H₅₇N₅O₇ and the molecular weight is 719.91. It specifically functions as an inhibitor of the chymotrypsin-like activity of the 20S proteasome which leads to the accumulation of protein substrates within the cell and induction of apoptosis.

3.1.1 FORMULATION: Carfilzomib for Injection will be provided as a lyophilized powder which, when reconstituted, contains 2 mg/mL isotonic solution of CFZ Free Base in 10 mM sodium citrate buffer (pH 3.5) containing 10% (w/v) sulfobutylether- β -cyclodextrin (SBE β CD, Captisol®).

3.1.2 STORAGE Lyophilized Carfilzomib for Injection must be stored at 2–8°C in a securely locked area to which access is limited to appropriate study personnel. Additional drug information, in particular the Identified Risks of Carfilzomib, is contained in Appendix 20.1. Further information can be found in the product labelling.

3.2 Rituximab is a monoclonal antibody directed against the CD20 antigen on B-lymphocytes, approved for treatment of CD20-positive Non-Hodgkin Lymphomas (NHL). Rituximab will be obtained from a commercial source.

4.0 STAGING CRITERIA

Staging and response assessment will follow the guidelines of the VIth International Workshop for WM (Appendix 20.2 and 20.4), the Lugano criteria for nodal lymphoma²³ and for spleen-only disease will follow guidelines of Matutes and colleagues.²⁴

5.0 ELIGIBILITY CRITERIA

Patients with Waldenström Macroglobulinemia or Marginal Zone lymphoma who meet inclusion/exclusion criteria below are eligible.

At least 5 patients with rituximab-refractory disease will be enrolled (best response of stable disease or progression while on treatment with, or progression within 6 months of, rituximab-containing therapy). Accrual will be modified to ensure 5 rituximab-refractory patients are enrolled, without enrolling more than 24 total patients.

5.1 Inclusion Criteria

- Waldenström's macroglobulinemia (WM) or marginal zone lymphoma (MZL) based on institutional pathology review; see Appendix 20.3 for WM criteria. Patients may have either previously untreated or relapsed/refractory disease.
- Measurable disease: for WM presence of monoclonal IgM immunoglobulin concentration on serum electrophoresis, with lymphoplasmacytic marrow infiltrate; for MZL: measurable nodal disease measuring at least 1.5 cm in longest dimension, or splenomegaly.

- Indication for initiation of therapy, as defined in protocol section 5.3
- Age greater than or equal to 18 years old
- Adequate hematopoiesis, including ANC >1,000/ μ L and platelet count >75,000/ μ L unless disease-related (due to marrow infiltration or splenomegaly).
- Serum creatinine <2.5 mg/dL or creatinine clearance >30 cc/min.
- Bilirubin <2 x ULN and AST and ALT <3 x ULN.
- All patients must be informed of the investigational nature of this study and have given written consent in accordance with institutional and federal guidelines.
- Expected survival of >90 days.
- Females of childbearing potential (FCBP) must agree to pregnancy testing and to practice contraception.
- Male subjects must agree to practice contraception.

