7.2 Administration of Rituximab to CFZ Non-responders

Subjects who fail to achieve at least a 25% M-protein reduction based on SPEP m-protein quantification for WM, or partial response for MZL based on imaging, following 2 cycles of CFZ therapy will receive rituximab concurrent with CFZ.

7.2.1 Note: the bone marrow aspirate / biopsy after cycle 2 is exploratory and not to be used for response assessment or determination regarding rituximab.

7.2.2 IV Rituximab, pre-medications, and hypersensitivity management will be administered according to standard institutional or pharmacy guidelines.

| RITUXIMAB weekly x 4 doses (cycle 3) then monthly (cycles 4-6) | | | | |
|---|---|------|------|------|
| Treatment | Cycle 3-6 for patients not responding to CFZ (actual dates may vary +/- 3 days; cycle timing refers to CFZ) | | | |
| | C3 D1,8,15,22 | C4D1 | C5D1 | C6D1 |
| Rituximab 375 mg/m ² | X, X, X, X | X | X | X |

7.2.3 Following rituximab administration for WM, weekly laboratory evaluation of IgM levels (to evaluate for Ig M flare for clinical and study data purposes) is required. (See section 10, study calendar). As clinically indicated, viscosity measurement and other evaluation or management of hyper-viscosity syndrome, including plasmapheresis, should be undertaken. Weekly evaluation will continue until no longer clinically indicated.

7.3 Criteria for removal from protocol treatment: (Note: Subjects discontinued from CFZ will not receive rituximab on study.)

7.3.1 Symptomatic progression of disease after completion of at least 4 total cycles of CFZ therapy (with or without rituximab). IgM flare following rituximab (even if requiring plasmapheresis), or biochemical progression alone do not require removal from protocol treatment.

- 7.3.2 Inability to tolerate more than 20 mg/m² of CFZ during the first 4 doses of therapy, despite maximal supportive care.
- 7.3.3 Development of excess hematologic toxicity not responding to supportive care or persisting despite dose reductions—as outlined in Section 8.0
- 7.3.4 Development of any other unacceptable toxicities unless prophylactic measures can be taken for subsequent cycles.
- 7.3.5 Missed doses will not be replaced during a cycle. If a subject misses more than 2 doses of any cycle for reasons other than toxicity, the subject will be discontinued.
- 7.3.6 Delay of a treatment cycle for more than 4 weeks due to adverse events

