8.2.4 Dose Reductions for Non-Hematologic Toxicities

- Study drug should be held for \geq Grade 3 events until resolved to \leq Grade 1 or return to baseline, unless otherwise noted in the table below.
- All cases of grade 3 or greater systolic HTN (SBP >160) will require action per protocol including holding study drug and management /dosing only once BP is controlled.
- After resolution of the event to \leq Grade 1 or return to baseline, if the adverse event was not treatment-related, subsequent treatment with CFZ may resume at full dose. If the event was treatment-related, subsequent treatment with CFZ will resume at dose level -1. If toxicity continues or recurs, a 2nd CFZ dose reduction to dose level -2 may be permitted the discretion of the investigator. No more than two dose reductions will be permitted in an individual subject on study. If toxicity continues or recurs after two dose reductions, the subject should be removed from study.
- Dose adjustment guidelines for non-hematologic toxicities are summarized in the following table:

| Symptom | Recommended Action Carfilzomib |
|---|--|
| Allergic reaction/hypersensitivity Grade 2 – 3 | Hold until \leq Grade 1, reinstitute at full dose. |
| Grade 4 | Discontinue |
| Grade 3 or higher systolic HTN | Hold until grade 2 or less, initiate medical management if clinically indicated, dose only when resolves or improves to Grade 2 or less. |
| Tumor lysis syndrome (\geq 3 of following: \geq 50% increase in creatinine, uric acid, or phosphate; \geq 30% increase in potassium; \geq 20% decrease in calcium; or \geq 2-fold increase in LDH | Hold CFZ until all abnormalities in serum chemistries have resolved. Reinstigate at full doses. |

| | |
|---|--|
| Infection Grade 3 or 4 | Hold CFZ until systemic treatment for infection complete. If no neutropenia, restart at full dose. If neutropenic, follow neutropenic instructions. |
| Herpes zoster or simplex of any grade | Hold CFZ until lesions are dry. Re institute at full dose |
| Gr 2 treatment emergent neuropathy with pain | Continue to dose. If neuropathy persists for more than two weeks hold CFZ until resolved to \leq Gr 2 without pain. Then restart at 1 dose decrement |
| Grade 3 neuropathy | Withhold CFZ until resolved or returned to baseline. Subsequent treatment with carfilzomib should resume at a lower dose level. |
| Grade 4 neuropathy | Discontinue |

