| Renal Dysfunction CrCl \leq 15 mL/min | Hold until CrCl $>$ 30 mL/minute; restart at 1 dose decrement |
| Congestive heart failure | Any subject with symptoms of congestive heart failure, whether or not drug related, must have the dose held until resolution or return to baseline, after which treatment may continue at a reduced dose, or the subject may be withdrawn from the study. If this results in a delay of treatment for more than 4 weeks, the subject will be withdrawn from the study. |
| Other non-hematologic toxicity assessed as CFZ-related \geq Grade 3 | Hold dose until toxicity resolves to \leq Grade 1 or baseline. Restart at 1 dose decrement. |

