8.2.7 Dosing Modifications

Dose modifications and delays different from those stated in the protocol, for management of toxicities, will be permitted at the discretion of the Investigator.

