8.2.8 Safety Considerations

Based upon the experience in the Phase 1 and 2 clinical studies with CFZ, the following observations are noted:

- A "first dose effect" has been seen, which is notable for fever, chills, rigors, and/or dyspnea occurring during the evening following the first day of infusion and an increase in creatinine, which may be the clinical sequelae of rapid tumor lysis and/or cytokine release.
- Should a "first dose" effect occur at any point during Cycle 1 or 2, treatment with high dose glucocorticoids (e.g. methylprednisolone 50–100 mg) is recommended. In addition, intravenous fluids, vasopressors, oxygen, bronchodilators, and acetaminophen should be available for immediate use and instituted, as medically indicated.
- Dexamethasone 8 mg PO/IV will be administered prior to all CFZ doses during the 1st cycle.
- If treatment-related fever, rigors, chills, and/or dyspnea are observed post any dose of CFZ after dexamethasone has been discontinued, dexamethasone should be re-started and administered prior to subsequent doses.
- CrCl changes are mostly transient, reversible, and non-cumulative. All subjects should be well hydrated. Clinically significant electrolyte abnormalities should be corrected prior to dosing with CFZ. Renal function must be monitored closely during treatment with CFZ. Serum chemistry values, including creatinine, must be obtained and reviewed prior to each dose of CFZ during Cycles 1 and 2. Carfilzomib must be held for subjects with a CrCl < 15 mL/min at any time during study participation.
- Subjects with active or suspected infection of any kind that required systemic treatment should not be dosed with CFZ until the infection has resolved and if being treated with anti-infective, the course of antibiotics has been completed.
- Carfilzomib treatment can cause nausea, vomiting, diarrhea, or constipation sometimes requiring the use of anti-emetics or anti-diarrheals. Fluid and electrolyte replacement should be administered to prevent dehydration.

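### Renal entry can be met on serum creatinine alone, while the carfilzomib hold and restart rules use creatinine clearance, so an eligible patient may be unable to restart at baseline function or, uncommonly, be on hold at entry

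*Combined protocol and SAP*

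**What the plan says.** **Entry.** Section 5.1 requires "Serum creatinine <2.5 mg/dL or creatinine clearance >30 cc/min". The two tests are alternatives. Section 5.2 lists no renal exclusion, so a patient who qualifies on creatinine faces no CrCl floor.

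**Hold.** The renal row of the 8.2.4 table applies at CrCl of 15 mL/min or less. Section 8.2.8 sets a slightly different boundary: "Carfilzomib must be held for subjects with a CrCl < 15 mL/min at any time during study participation".

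**Restart.** Only the 8.2.4 table gives a restart level. Dosing resumes once CrCl is above "30 mL/minute; restart at 1 dose decrement". The general instruction ahead of the table would accept a return to baseline, but it gives way where the table states something else, and the renal row does.

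**Removal and discretion.** Section 7.3.6 lists as a ground for removal from treatment: "Delay of a treatment cycle for more than 4 weeks due to adverse events". Section 8.2.7 adds: "Dose modifications and delays different from those stated in the protocol, for management of toxicities, will be permitted at the discretion of the Investigator".

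No section says how CrCl is to be calculated or measured.

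**The concern.** Entry and dosing are governed by different quantities. The CrCl alternative in 5.1 (above 30) matches the restart level. The creatinine alternative does not, because a given creatinine corresponds to very different clearances depending on age, weight and sex. The plan can therefore admit two kinds of patient whom its dosing rules do not fit:

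- a patient whose CrCl at entry is already at or below the hold boundary;
- a patient with CrCl of about 15 to 30, who can be dosed but who, after a renal hold, must reach better renal function than at enrolment before restarting.

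Reduced renal function at entry is foreseeable, since 5.3.1 lists nephropathy related to Waldenström's among the indications for treatment. What is at stake is consistent handling of such patients in a 24-patient single-arm trial whose primary endpoint is read after cycle 2. Section 8.2.8 requires creatinine review before every dose in cycles 1 and 2, so the hold rule would operate in that same window.

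**Working it through.** The plan gives no figure on this point, so there is none to reproduce. The check asks whether the conflict exists in the text, whether it can occur, and what then follows.

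**1. The passages side by side**

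| Step | Section | Quantity | Boundary | Baseline accepted? |
|---|---|---|---|---|
| Entry | 5.1 | creatinine, or CrCl | below 2.5 mg/dL, or above 30 | not applicable |
| Hold | 8.2.4 table | CrCl | 15 or less | not applicable |
| Hold | 8.2.8 | CrCl | below 15 | not applicable |
| Restart | 8.2.4 table | CrCl | above 30 | no |

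A CrCl of exactly 15 is a hold under 8.2.4 and not under 8.2.8.

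**2. Can creatinine below 2.5 go with CrCl of 30 or less?** Assumption: Cockcroft-Gault, CrCl = (140 − age) × weight / (72 × creatinine), × 0.85 for women. With age, weight and sex fixed, CrCl is inversely proportional to creatinine. The creatinine that gives CrCl of 30 or 15 is therefore k/30 or k/15, where k = (140 − age) × weight / 72, × 0.85 for women.

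| Patient (all eligible) | Entry creatinine | Calculation | CrCl | Creatinine at CrCl 30 | Creatinine at CrCl 15 |
|---|---|---|---|---|---|
| Man, 70 y, 70 kg | 2.4 | 70×70/(72×2.4) | 28.4 | 2.27 | 4.54 |
| Woman, 80 y, 60 kg | 1.6 | 0.85×60×60/(72×1.6) | 26.6 | 1.42 | 2.83 |
| Woman, 70 y, 60 kg | 2.0 | 0.85×70×60/(72×2.0) | 24.8 | 1.65 | 3.31 |
| Woman, 75 y, 60 kg | 2.4 | 0.85×65×60/(72×2.4) | 19.2 | 1.53 | 3.07 |
| Woman, 80 y, 50 kg | 2.4 | 0.85×60×50/(72×2.4) | 14.8 | 1.18 | 2.36 |

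For all five, the creatinine at CrCl 30 is lower than the entry value, so none meets the restart level at baseline. The last patient is on hold before the first dose under both 8.2.4 and 8.2.8.

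**3. Range.** Over ages 60 to 90 and weights 45 to 80 kg, both sexes, CrCl runs from 11.1 to 37.0 mL/min at creatinine 2.4 and from 13.3 to 44.4 at creatinine 2.0. Values below 30 are common in that grid. Values of 15 or less appear only from age 75 upward and at 60 kg or less. A 65-year-old of 70 kg would need creatinine of about 4.1 (woman) or 4.9 (man) to reach 15, far above the entry limit.

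**4. How far is the hold boundary for those who can be dosed?** The required rise in creatinine is the CrCl at entry divided by 15, minus 1: 28.4/15 gives +89%, 26.6/15 gives +77%, 24.8/15 gives +65%, and 19.2/15 gives +28%.

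**5. What follows under 7.3.6?** It covers delays caused by adverse events. Section 14.1 treats a condition with onset before consent as medical history, so a low CrCl already present at entry does not trigger it. Such a patient is held with no defined next step. For a patient entering between 15 and 30, removal requires an on-study fall to the hold boundary and then a cycle delay of more than 4 weeks.

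**The case against.** The case that this is minor has real force.

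- *Few patients would be affected.* Section 8.2.8 describes CrCl changes on carfilzomib as largely temporary. Appendix 20.1 reports Grade 2 creatinine rises in three of five myeloma patients at 27 mg/m², but says they reversed quickly, did not recur on rechallenge, and were all but removed in later studies by hydration and low-dose dexamethasone. Section 7.1.2 specifies both in cycle 1, with hydration subject to contraindication. Three of the four dosable examples above need creatinine to rise by 65% or more. This stands, and it limits the size of the point.
- *The investigator may deviate.* This also stands for a fall during treatment. Section 8.2.7 is worded for managing toxicities, however, and does not clearly reach a low CrCl that predates any drug.
- *The renal row is not unusual.* Only the Grade 3 neuropathy, heart failure and other-toxicity rows mention baseline; the allergy, hypertension, tumour lysis, infection, herpes and Grade 2 neuropathy rows do not. A restart level above the hold level may be a deliberate margin. That is fair: the missing baseline clause is not a fault in itself. The conflict comes from combining it with an entry test that sets no CrCl floor. For blood counts the protocol does pair the two ends: 5.1 waives the limits for disease-related cytopenias, and 8.1 accepts a return to baseline when they reflect marrow infiltration.
- *A held patient is not necessarily lost to the analysis.* A reader might infer that each such patient wastes one of the 9 futility places (1/9 = 11%) or one of the 24 (1/24 = 4%). The documents do not establish this. Section 12.2 counts assessable patients, response after cycle 2 rests on SPEP or CT, and 7.3.5 does not discontinue a patient for doses missed because of toxicity. A patient held in mid-cycle may still be assessed. No effect on type I error, power or the futility probability has been shown.

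**Conclusion.** The conflict holds as a matter of text. Creatinine alone admits a patient at any CrCl, the dosing rules use CrCl alone, and the restart level can lie above the patient's own entry value. The realistic form is entry at about 15 to 30 mL/min followed by a renal hold. Entry already on hold is permitted but uncommon, and under the assumed formula it needs an old and light patient. The two hold boundaries also contradict each other at exactly 15.

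Two stronger readings should be resisted. One is that the dosing rules cannot treat anyone below 30: patients between 15 and 30 can be dosed, and 8.2.7 leaves room after a hold. The other is that every such patient ends in removal under 7.3.6: that rule does not reach a pre-existing low CrCl, and reaches the others only after a fall and a long delay.

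The CrCl values depend on Cockcroft-Gault and on illustrative ages and weights. The documents do not allow an estimate of how many enrolled patients would be affected.

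**What to change.** Reconcile sections 5.1, 8.2.4 and 8.2.8 so that entry, hold and restart use compatible quantities and boundaries. State how CrCl is determined. Remove the difference between 15 or less and below 15. State what happens to a patient who meets 5.1 but is already at or below the hold boundary before the first dose. Which quantity, which limits and which restart condition apply is a clinical decision for the sponsor's clinicians, and none is proposed here.

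The cost is a few lines of amendment. If CrCl is to be calculated from serum creatinine, the metabolic panel already in the section 10 calendar supplies the value, so no new test is needed. Depending on how the passages are aligned, a few patients' eligibility or restart status may change.
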